Given the difficulty in randomizing patients (high cost of phenoxybenzamine has caused a large portion of patients crossing over to the doxazosin arm, resulting in unbalance between the number of patients in each arm), patients who have been pre-treated with doxazosin before pheochromocytoma resection prospectively followed during the course of this study will be compared to a retrospective group of patients who were pre-treated with phenoxybenzamine.

Descriptive statistics including mean, median, standard difference, and frequencies will be calculated for each of the variables measured.

Differences in hemodynamic instability as indexed by specific vital sign parameters, ICU length of stay, inpatient length of stay, morbidity, mortality, cost, and quality of life will be analyzed with t tests or non-parametric tests as appropriate.

1.3 *If you will conduct genetic analysis with specimens, provide your assurance that the results will not be disclosed to subjects or used for clinical care.

Agree	
Not Applicable	

2.0 *Describe specimens and/or data that will be acquired without direct contact with study participants. Complete this item for each type used in the study:

usea in the stu	uy.	
Source	Data and/or Specimens Information	
View UCLA medical records	Data and/or Specimens? Indicate all that apply:	Data
	Indicate whether the data and/or specimens are pre-existing, at the time of this study, and/or if collection will be prospective:	Pre-existing
	Describe the data and/or specimens and indicate the original collection dates:	Electronic medical records from patients undergoing adrenalectomy for pheochromocytoma or paraganglioma from January 1, 2015 to present. Please see item 4.0 for further details on data to be collected from the EMR.
	Indicate the approximate number of data records and/or specimens to be collected:	50
	Will the specimens be used with animals?	No
	If yes, indicate the IACUC Number:	No Value Entered

*If any sources of data and/or specimens are not at UCLA, provide your agreement that the appropriate institutional approvals for release will be obtained (e.g., IRB approval).

Agree

•	
Not Applicable	
	o third parties, please contact the CTSI for directions about additional requirements. sources/pages/third_party
nttps://www.ctsi.ucla.edu/researcher-re	sources/pages/third_party
uttps://www.ctsi.ucla.edu/researcher-re	

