PATIENT ACQUISITION. All patients referred to the UCLA Department of Surgery requiring surgical resection of pheochromocytoma or paraganglioma will be counseled about surgery and the necessity for preoperative alpha blockade. The benefits and risks of the study will discussed, and the patient will be given the opportunity to enroll. Upon obtaining informed consent regarding enrollment in the study, the patient will be randomized to either receive preoperative blockade with either phenoxybenzamine or doxazosin.

PREOPERATIVE PREPARATION. The patient will then be referred to the UCLA Preoperative Evaluation and Planning Center (PEPC) for preoperative planning and optimization by an attending anesthesiologist. Additional testing such as echocardiography or stress testing will be pursed in accordance with preoperative risk-stratification in the standard fashion. A few weeks prior to surgery, the patient will initiate preoperative alpha blockade with the drug as determined by randomization. The drug will be titrated to a blood pressure of 120-130/80-85 in the standard fashion. Adjunctive beta blockers or calcium channel blockers may be initiated at the discretion of the physician.

Titration will be performed utilized the attached log ("Medication and Blood Pressure Log"), which will be emailed to the patient and will be returned by the patient by email every 2 days. The patients sitting and standing blood pressure will be used to titrate their alpha blocker dosage to prespecified targets as noted in the original IRB proposal. Heart rate will be logged to determine whether the patient requires adjunctive

specified targets as noted in the original IRB proposal. Heart rate will be logged to determine whether the patient requires adjunctive antihypertensive medications such as beta blockers or calcium channel blockers. This titration will take place over a period of 2-3 weeks. Once the patient's alpha blockade titration is complete, the log will be saved in a secure, encrypted server and will be linked with the patients record using non-identifying record ID.

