 Eligibility for the study will be evaluated during the time of surgical consultation by review of prior medical records including biochemical tests and imaging by the attending surgeon.

We expect 100% of patients evaluated for pheochromocytoma resection will be eligible for the study.

Assuming an enrollment rate of 85%, 73 patients will have to be screened to meet our target sample size of 62 patients.

ID: IRB#17-000048

View: NEW 11.2 - Characteristics of Study Population

This view has been locked by amendment(s)

Warning: Save your work at least every 15 minutes by clicking "Save" or "Continue."

-Cha	Characteristics of Study Population		
1.0	icate the age range of the study participants.		
	ck all that apply:		
	0 to 6 years		
	7 to 11 years		
	12 to 17 years		
	17 or younger in California who can consent for themselves - see note below		
	17 or younger outside California who can consent for themselves - see note below		
	18 years or older		
	TE:		
	 For additional information on minors in California who are permitted to consent for themselves please refer to the section "Legal Exceptions Permitting Certain Minors to Consent" in the OHRPP Guidance document, Child Assent and Permission by Parents or Guardians For additional information on minors outside of California who are permitted to consent for themselves please refer to the section "Exceptions Outside of California" in the OHRPP Guidance document, Child Assent and Permission by Parents or Guardians 		
2.0	icate if any of the following populations/specimens will be specifically recruited/obtained for the study. Adults who are competent to give informed consent		
	Adults unable to give informed consent		
	Adults with diminished capacity to consent		
	Fetal Tissue		
	Neonates		
	Participants Unable to Read, Speak, or understand English		
	Pregnant Women/Fetuses		
	Prisoners		
	UCLA Faculty/Staff		
	UCLA Students		
	Wards		
	Unknown/Not Applicable		
3.0	t possible that there may be non-English speakers enrolled in this study or children whose parents are non-English speaking? Yes O No		
	View NEW 40.4 Obilders (Misses)		

ID: IRB#17-000048 View: NEW 12.1 - Children (Minors)

This view has been locked by amendment(s)

Warning: Save your work at least every 15 minutes by clicking "Save" or "Continue."

*Ch	oose the	description that is applicable to this study:
	The res	earch does not involve greater than minimal risk (45 CFR 46.404/21 CFR 50.51)

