Interim safety analysis will be performed at the point at which 50% of the targeted cohort has been followed-up for 30 days.

- *Have stopping rules been established for the study?
 - O Yes O No
 - 4.1 If yes, describe or indicate where the information can be found in the attached protocol.

The primary outcomes that will be compared at the interim safety analysis include postoperative morbidity as manifested by rates of stroke and myocardial infarction as well as postoperative mortality within 30 days. Rates of stroke, myocardial infarction, and mortality will be compared with the chi square test and the study will be stopped if a significant difference is found with a threshold of P < 0.05.

*Are there defined rules for withdrawing participants from study interventions?

O Voc A Na

○ Yes •	No	
5.1	If yes, describe or indicate where the information can be found in the attached protocol.	
ID: IRB#17-000048	View: NEW 16.1 - Payment, Costs, and Injury	

	heck all tha	t anniv
		nent will be provided
	Universi	y check
	Course	Credit
	Cash	
	Gift Card	Is/Bruincard Deposit
	Non-Moi	netary Gifts or Services
	Other (in	cluding vouchers for parking)
	1.1	If you selected Non-Monetary Gifts or Services or Other, describe:
	1.2	If you selected Cash and/or Gift Cards/Bruincard Deposit please specify the estimated total amount of money you will require to pay all participants during the length of the entire study. This information is required by UCLA Business and Finance Services (BFS), the office that will provide the cash/gift cards for payment.
	orovide th - If a whe - If th - If fa	articipants will receive financial or other payment for their participation in the study, please e following information: oplicable, the amount each participant will receive and the payment schedule to be followed including ther partial payment will be provided when the participant does not complete the study. Here are different plans for different populations or sub-studies, specify the groups and describe the plans milies or children will be involved in the research, clarify how the payments, items or services will be ortioned.
*	Will subje	cts incur any financial obligations from participation in the study? No
	3.1	If yes, describe:

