		 Research participants will not be asked to sign a consent form or give oral consent 			
		Consent will be obtained by a collaborating institution.			
		1.1	- If you checked more than one plan above, list the study groups and the plan that you will use for each If you checked "Consent will be obtained by a collaborating institution", explain the consent process and upload a copy of the most recent approved consent document in item 1.2. Signed consent obtained from patients who were randomized to phenoxybenzamine or doxazosin. Requesting a waiver of consent for the retrospective cohort of patients who were pre-treated with phenoxybenzamine. If applicable, attach the consent document(s) from collaborating institution(s).		
			Document Name Document Version # There are no items to display		

View: NEW 20.3 - Description of the Consent Process

ID: IRB#17-000048

This view has been locked by amendment(s)

Warning: Save your work at least every 15 minutes by clicking "Save" or "Continue."

.0	*Indicate the	type of setting(s) in which the consent process will be conducted.
	Check all that	apply.
	☐ In a priva	
	In a priv	ate room
	☐ In a waiti	ng room
	n a publ	ic setting
	☐ In a grou	p setting
	On the ir	ternet
	✓ Over the	telephone
	Other	 
	1.1	If you checked more than one response, or indicated other, describe.
		If a patient meets inclusion criteria for the study, the study will be
		discussed with the patients at the time of surgical consultation in
		a private exam room by the attending surgeon and informed consent obtained at that time.
		If a patient has been already evaluated for surgery but has not yet received surgery and the study has not been introduced, a phone
		call will be made to the patient by an MD to discuss the study
		over the phone. The patient will be mailed a consent form to either return by mail or in person at their next visit.
		Cities return by mail of in person at their next visit.
		All patients enrolled in the study will have had an in person encounter with an attending surgeon prior to obtaining consent.
		encounter with an attending surgeon prior to obtaining consent.
	1.2	If the setting is not private, describe the measures to protect
.0		confidentiality or indicate "not applicable." measures that will be taken to provide prospective research participants with sufficient opportunity to consider whether or

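### The interim stopping rule applies an asymptotic chi-square test at expected counts too small for it, and under the revised design it would also stop the study because historical controls did worse

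*Combined protocol and SAP*

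**What the plan says.** Section 15.2 (Data & Safety Monitoring Plan), item 3.1, sets the timing: "Interim safety analysis will be performed at the point at which 50% of the targeted cohort has been followed-up for 30 days". Item 4.1 names stroke, MI and mortality within 30 days and states that "mortality will be compared with the chi square test and the study will be stopped if a significant difference is found", with P below 0.05 as the threshold. It defines no composite, so I read three separate tests. It names no version of the chi-square test, no provision for small counts, no direction and no comparator group.

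Section 11.1, item 6.0, gives the planned size: "73 patients will have to be screened to meet our target sample size of 62 patients".

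The design is described in two ways. Section 9.6, item 1.2, reports "a large portion of patients crossing over to the doxazosin arm, resulting in unbalance between the number of patients in each arm", and says that prospectively followed doxazosin patients "will be compared to a retrospective group of patients who were pre-treated with phenoxybenzamine". Section 10.1 (Research Design and Methods, patient acquisition) still says that "the patient will be randomized to either receive preoperative blockade with either phenoxybenzamine or doxazosin". Section 20.1, item 1.1, refers to patients already randomised: "Signed consent obtained from patients who were randomized to phenoxybenzamine or doxazosin". The retrospective source in section 9.6, item 2.0, is about 50 records, described as "Electronic medical records from patients undergoing adrenalectomy for pheochromocytoma or paraganglioma from January 1, 2015 to present".

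**The concern.** The chi-square P-value is a large-sample approximation. At a look of about 31 patients with rare events, the tables that decide whether the study stops have very small expected counts. Two consequences follow. The decision can turn on which version the analyst's software applies, and the uncorrected version does not hold its nominal 5%.

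The rule also has no direction. That suits two randomised arms, where patients in either arm may need protection. Once the comparator is a group of past patients, an excess of events in that group would also stop the study, although nobody still to be treated belongs to it. Because the rule was not restated for the revised design, neither its denominator nor its comparator can be read from the text.

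**Working it through.** **The plan's own figure.** 62 / 0.85 = 72.9, so 73 screened, as stated. The documents give no power or operating characteristic for the interim look.

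**Look size.** 0.50 × 62 = 31, if the targeted cohort is the 62.

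**Assumptions.** The documents give no event rates, arm counts or number of phenoxybenzamine controls. For the randomised reading I use 16 v 15. For the historical reading I use 31 doxazosin patients v 25, 35 or 50 controls. Fifty is an upper illustration, because the 50 records cover all resections since 2015. Event rates of 2%, 5% and 10% are illustrative.

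**Expected counts at first-trigger tables** (total events × smaller group / N): 4×15/31 = 1.94; 3×31/81 = 1.15; 6×31/81 = 2.30; 3×25/56 = 1.34; 1×6/31 = 0.19.

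**Same data, two versions.** For a/n v b/m with N = n+m, k = a+b and D = |a(m−b) − b(n−a)|, Pearson is X² = N·D² / [n·m·k·(N−k)]. Yates replaces D by D − N/2.

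- 4/16 v 0/15: D = 60. Pearson 31×60²/(16×15×4×27) = 4.31, P=0.038. Yates 31×44.5²/25,920 = 2.37, P=0.124.
- 3/31 v 0/50: D = 150. Pearson 81×150²/(31×50×3×78) = 5.02, P=0.025. Yates 81×109.5²/362,700 = 2.68, P=0.102.
- 1/6 v 0/25 (illustrative strong imbalance): D = 25. Pearson 31×25²/(6×25×1×30) = 4.31, P=0.038. Yates 31×9.5²/4,500 = 0.62, P=0.430.

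**Operating characteristics per endpoint**, by exact enumeration of two binomials. Size is the maximum over all common event rates. In the 10% v 2% columns the first-named group has the excess.

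| Split | Versions disagree, 2% in both | Versions disagree, 10% v 2% | Pearson maximum size | Pearson stops, 10% v 2% | Two-sided Barnard stops, 10% v 2% |
|---|---|---|---|---|---|
| 16 v 15 | 0.03% | 4.9% | 7.1% | 5.1% | 5.1% |
| 31 v 25 | 0.7% | 10.7% | 5.9% | 12.7% | 12.0% |
| 31 v 35 | 0.2% | 11.2% | 5.3% | 21.9% | 21.9% |
| 31 v 50 | 0.9% | 20.6% | 5.3% | 38.0% | 38.0% |

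Barnard's maximum size is 4.6% to 5.0% at these splits. At the illustrative 6 v 25, Pearson's maximum size is 8.7%, and one event in the small arm stops the study. At 2% in both arms the false-stop rate there is 7.1% by Pearson, 0.35% by Yates and 0.52% by two-sided Barnard (P=0.087 for the single event, so continue).

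**Direction, historical design.** 0/31 v 6/50: D = 186, 81×186²/(31×50×6×75) = 4.02, P=0.045, stop. 0/31 v 3/25: P=0.047, stop. The chance per endpoint that Pearson stops the study because controls did worse (31 v 25, 31 v 35, 31 v 50) is:

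- 2% in both: 0.7%, 0.03%, 0.03%
- 5% in both: 2.8%, 0.6%, 0.8%
- 2% doxazosin v 5% controls: 7.0%, 1.6%, 2.0%
- 2% doxazosin v 10% controls: 28.2%, 16.3%, 22.5%

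**The case against.** The strongest reply is that the practical effect of the test version is small and partly constructed. Much of this stands.

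- A reader might infer that Pearson and Yates generally conflict at small expected counts. They do not. With three events v none at 15 v 16 neither stops; with five v none in the arm of 15 both stop; and they can also disagree at expected counts above 3. They differ only at boundary tables.
- A reader might take the share of Pearson stops that Yates would overturn (51% to 95% at 10% v 2%) as the size of the problem. That share is conditional on a Pearson stop under an assumed five-fold excess. At 5% v 2% the unconditional disagreement is 0.5%, 1.3%, 2.6% and 7.3% across the four splits.
- The 6 v 25 split is an illustration. Section 9.6 reports imbalance without counts, and from 7 v 24 to 11 v 20 Pearson's false stops at 2% in both arms fall to 0.5% to 1.3%. That split belongs to the randomised reading and the direction point to the historical one, so the two effects should not be added.
- Pearson's maximum size arises over all event rates. At 5% in both groups its false-stop rate is 0.57% at 15 v 16 and 3.8% at 31 v 50, both below nominal.
- Stopping on any difference is a legitimate choice for randomised arms.
- Section 10.1 lists attachments that I have not seen. Item 4.1 invites a pointer to an attached protocol, but the sponsor gave a description and no pointer.

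The choice of method is not answered by this. A binding rule should give one decision on one dataset and hold its stated level. An exact test does both at almost no cost in sensitivity. Nor does the reply explain why an excess among past controls should stop a prospective doxazosin study.

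**Conclusion.** The concern holds in a limited form and should be fixed before the interim look. The chi-square test is the wrong tool at the tables that decide a stop. Its version can reverse the decision there, and uncorrected Pearson exceeds 5% at its maximum (5.3% to 7.1% at the four main splits). Under assumed rates the versions disagree in well under 1% of looks per endpoint when both groups are at 2%, and in about 5% to 21% at 10% v 2%. Under the section 9.6 design, the rule as written can also stop the study in doxazosin's favour against past controls.

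The boundary P-values depend only on the tables. The probabilities depend on my assumed event rates and group sizes, and the 31 depends on reading the targeted cohort as the 62. The documents do not support a claim that the unnamed version usually decides the outcome, or that the actual arms are as unbalanced as 6 v 25. The undefined cohort, comparator and version would, on their own, be gaps to fill in the text.

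**What to change.** Replace the test in section 15.2, item 4.1, with a named exact test. For example:

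> Stroke, myocardial infarction and 30-day mortality will each be compared by Barnard's exact unconditional test (pooled statistic) at two-sided P < 0.05. For prospective doxazosin v retrospective phenoxybenzamine, the study stops only if the excess is on doxazosin. For any comparison of randomised groups, an excess in either group stops the study.

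Barnard's test orders tables by Pearson's statistic and gives it an exact P-value: 0.040 at 4/16 v 0/15 and 0.027 at 3/31 v 0/50, so both stops are kept. Fisher's test is simpler but less sensitive at 10% v 2%: 5.3% v 12.0% at 31 v 25, and 22.6% v 38.0% at 31 v 50.

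Keeping the two-sided threshold while acting in one direction means that false stops for harm do not rise. At 31 v 35 with 5% in both groups, the present rule (Pearson) gives 5.6% over three endpoints taken as independent, or 1 − (1 − 0.056)^(1/3) = 1.9% each. Removing the 0.6% that favours doxazosin leaves about 1.3% each, or about 4% over three. A one-sided P<0.05 would instead give 11.3% with Barnard's test. That threshold, Boschloo's test and a composite endpoint are options for the sponsor only.

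When rewording, state in item 3.1 what the targeted cohort now is. State also which phenoxybenzamine patients form the interim comparator (retrospective, randomised or both; as randomised or as treated) and how many there are. Reconcile section 9.6, item 1.2, section 10.1 and section 15.2 accordingly.

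The cost is two short paragraphs and no extra data. A stop for a difference favouring doxazosin over historical controls is given up. No choice of test makes a 16 v 15 look sensitive: even Barnard's stops in only 5.1% of looks at 10% v 2%.

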	3.1 If other, describe
4.0	Indicate why the research could not practicably be carried out without a waiver of consent.
	The identities of the potential study participants who would meet the criteria for this study would not be known without access to their medical records
	Other 4.1 If other, specify
5.0	ION-UC INSTUTITION(S) / AGENCY(IES) HIPAA POLICIES AND PROCEDURES
	your research will involve access, use, or disclosure of PHI held by a non-UC institution/agency, please provide your assurances that you will omply with that (those) instutition(s)/agency(ies)' HIPAA policies and procedures.
	Agree
); IRR	7-000048 View: NEW 19.1 - Eligibility Screening

ID: IRB#17-000048

12/15/21, 8:26 AM 35 of 48

Eligibility Screening				
Lingi	binty ocicenning			
1.0	*Will you be conducting a preliminal recruitment process? Yes No	ry assessment with potential research participants to determine study eligibility during the		
ID : IRB#17-000048		View: NEW 20.1 - Informed Consent Process		

This view has been locked by amendment(s)

Warning: Save your work at least every 15 minutes by clicking "Save" or "Continue."

-Info	rmed	d Consent	Process———————————————————————————————————		
You ii 12.2/i			s (and/or minors who are permitted to consent for themselves) are participating in the study (Section 11.2/item 1.0 or Section		
			ation on minors who are permitted to consent for themselves please refer to the section "Legal Exceptions inors to Consent" in the OHRPP Guidance document, Child Assent and Permission by Parents or Guardians.		
1.0	*Inc	licate your p	plans for obtaining informed consent for this study.		
	Check all that apply:				
		Signed consent will be obtained from the research participant or Legally Authorized Representative.			
	 Signed consent means research participants will be asked to sign and date a written consent form. 				
		A waiver of signed consent is requested for the entire study. One of the following procedures will be conducted:			
		• A written information sheet will be used. Signed consent will not be obtained from research participants.			
· · · · · · · · · · · · · · · · · · ·			Il consent will be obtained from the research participant or Legally Authorized Representative (LAR)		
This option should be selected if the study involves consenting participants via the internet.		s option should be selected if the study involves consenting participants via the internet.			
		A waiver o	of consent is being requested.		
		 Research participants will not be asked to sign a consent form or give oral consent 			
		Consent will be obtained by a collaborating institution.			
		1.1	- If you checked more than one plan above, list the study groups and the plan that you will use for each If you checked "Consent will be obtained by a collaborating institution", explain the consent process and upload a copy of the most recent approved consent document in item 1.2. Signed consent obtained from patients who were randomized to phenoxybenzamine or doxazosin. Requesting a waiver of consent for the retrospective cohort of patients who were pre-treated with phenoxybenzamine. If applicable, attach the consent document(s) from collaborating institution(s).		
			Document Name Document Version # There are no items to display		

View: NEW 20.3 - Description of the Consent Process

ID: IRB#17-000048

This view has been locked by amendment(s)

Warning: Save your work at least every 15 minutes by clicking "Save" or "Continue."

.0	*Indicate the	type of setting(s) in which the consent process will be conducted.
	Check all that	apply.
	☐ In a priva	
	In a priv	ate room
	☐ In a waiti	ng room
	n a publ	ic setting
	☐ In a grou	p setting
	On the ir	ternet
	✓ Over the	telephone
	Other	 
	1.1	If you checked more than one response, or indicated other, describe.
		If a patient meets inclusion criteria for the study, the study will be
		discussed with the patients at the time of surgical consultation in
		a private exam room by the attending surgeon and informed consent obtained at that time.
		If a patient has been already evaluated for surgery but has not yet received surgery and the study has not been introduced, a phone
		call will be made to the patient by an MD to discuss the study
		over the phone. The patient will be mailed a consent form to either return by mail or in person at their next visit.
		Cities return by mail of in person at their next visit.
		All patients enrolled in the study will have had an in person encounter with an attending surgeon prior to obtaining consent.
		encounter with an attending surgeon prior to obtaining consent.
	1.2	If the setting is not private, describe the measures to protect
.0		confidentiality or indicate "not applicable." measures that will be taken to provide prospective research participants with sufficient opportunity to consider whether or
.0	Check all that Member an oral 6	confidentiality or indicate "not applicable." measures that will be taken to provide prospective research participants with sufficient opportunity to consider whether or pate in the study. apply. (s) of the study staff will meet with the prospective participants/families to review the consent document(s) and/or provide explanation of the study. Individuals will be given a chance to ask questions before making a considered decision about
.0	Check all that Member an oral e whether	confidentiality or indicate "not applicable." measures that will be taken to provide prospective research participants with sufficient opportunity to consider whether or pate in the study. apply. (s) of the study staff will meet with the prospective participants/families to review the consent document(s) and/or provide explanation of the study. Individuals will be given a chance to ask questions before making a considered decision about or not to participate in the study. tive participants/families will have the opportunity to take the consent form(s) home and may discuss the documents with
.0	Check all that Member an oral e whether Prospec others p	confidentiality or indicate "not applicable." measures that will be taken to provide prospective research participants with sufficient opportunity to consider whether or pate in the study. apply. (s) of the study staff will meet with the prospective participants/families to review the consent document(s) and/or provide explanation of the study. Individuals will be given a chance to ask questions before making a considered decision about or not to participate in the study.
.0	Check all that Member an oral e whether Prospec others p	confidentiality or indicate "not applicable." measures that will be taken to provide prospective research participants with sufficient opportunity to consider whether or nate in the study. apply. (s) of the study staff will meet with the prospective participants/families to review the consent document(s) and/or provide explanation of the study. Individuals will be given a chance to ask questions before making a considered decision about or not to participate in the study. tive participants/families will have the opportunity to take the consent form(s) home and may discuss the documents with rior to deciding whether or not to participate in the study.
.0	Check all that Member an oral e whether Prospec others p Prospec	confidentiality or indicate "not applicable." measures that will be taken to provide prospective research participants with sufficient opportunity to consider whether or nate in the study. apply. (s) of the study staff will meet with the prospective participants/families to review the consent document(s) and/or provide explanation of the study. Individuals will be given a chance to ask questions before making a considered decision about or not to participate in the study. tive participants/families will have the opportunity to take the consent form(s) home and may discuss the documents with rior to deciding whether or not to participate in the study.
.0	Check all that Member an oral e whether Prospec others p Other	measures that will be taken to provide prospective research participants with sufficient opportunity to consider whether or pate in the study. apply. (s) of the study staff will meet with the prospective participants/families to review the consent document(s) and/or provide explanation of the study. Individuals will be given a chance to ask questions before making a considered decision about or not to participate in the study. tive participants/families will have the opportunity to take the consent form(s) home and may discuss the documents with rior to deciding whether or not to participate in the study. tive participants will self-administer the consent and send it back if they decide to participate in the study.
.0	Check all that Member an oral e whether Prospec others p Prospec	confidentiality or indicate "not applicable." measures that will be taken to provide prospective research participants with sufficient opportunity to consider whether or nate in the study. apply. (s) of the study staff will meet with the prospective participants/families to review the consent document(s) and/or provide explanation of the study. Individuals will be given a chance to ask questions before making a considered decision about or not to participate in the study. tive participants/families will have the opportunity to take the consent form(s) home and may discuss the documents with rior to deciding whether or not to participate in the study.
.0	Check all that Member an oral e whether Prospec others p Other	measures that will be taken to provide prospective research participants with sufficient opportunity to consider whether or pate in the study. apply. (s) of the study staff will meet with the prospective participants/families to review the consent document(s) and/or provide explanation of the study. Individuals will be given a chance to ask questions before making a considered decision about or not to participate in the study. tive participants/families will have the opportunity to take the consent form(s) home and may discuss the documents with rior to deciding whether or not to participate in the study. tive participants will self-administer the consent and send it back if they decide to participate in the study.
.0	Check all that Member an oral e whether Prospec others p Other 2.1	measures that will be taken to provide prospective research participants with sufficient opportunity to consider whether or pate in the study. apply. (s) of the study staff will meet with the prospective participants/families to review the consent document(s) and/or provide explanation of the study. Individuals will be given a chance to ask questions before making a considered decision about or not to participate in the study. tive participants/families will have the opportunity to take the consent form(s) home and may discuss the documents with rior to deciding whether or not to participate in the study. tive participants will self-administer the consent and send it back if they decide to participate in the study. If you indicated other, describe.
	Check all that Member an oral e whether Prospec others p Other *Indicate the Patients will ha	measures that will be taken to provide prospective research participants with sufficient opportunity to consider whether or pate in the study. apply. (s) of the study staff will meet with the prospective participants/families to review the consent document(s) and/or provide explanation of the study. Individuals will be given a chance to ask questions before making a considered decision about or not to participate in the study. tive participants/families will have the opportunity to take the consent form(s) home and may discuss the documents with rior to deciding whether or not to participate in the study. tive participants will self-administer the consent and send it back if they decide to participate in the study. If you indicated other, describe.
.0	Check all that Member an oral e whether Prospec others p Other *Indicate the Patients will ha	measures that will be taken to provide prospective research participants with sufficient opportunity to consider whether or nate in the study. apply. (s) of the study staff will meet with the prospective participants/families to review the consent document(s) and/or provide explanation of the study. Individuals will be given a chance to ask questions before making a considered decision about or not to participate in the study. Individuals will have the opportunity to take the consent form(s) home and may discuss the documents with rior to deciding whether or not to participate in the study. It is participants will self-administer the consent and send it back if they decide to participate in the study. If you indicated other, describe. Rength of time subjects are given to decide whether they wish to participate in the study. ave approximately 1-2 weeks from the time of their initial surgical consultation to decide whether they wish to participate in the study assess whether subjects understand the information conveyed during the consent process?
.0	Check all that Check all that Member an oral e whether Prospec others p Other 2.1 *Indicate the Patients will ha *How will you Check all that	measures that will be taken to provide prospective research participants with sufficient opportunity to consider whether or nate in the study. apply. (s) of the study staff will meet with the prospective participants/families to review the consent document(s) and/or provide explanation of the study. Individuals will be given a chance to ask questions before making a considered decision about or not to participate in the study. Individuals will have the opportunity to take the consent form(s) home and may discuss the documents with rior to deciding whether or not to participate in the study. It is participants will self-administer the consent and send it back if they decide to participate in the study. If you indicated other, describe. Rength of time subjects are given to decide whether they wish to participate in the study. ave approximately 1-2 weeks from the time of their initial surgical consultation to decide whether they wish to participate in the study assess whether subjects understand the information conveyed during the consent process?
.0	Check all that Member an oral e whether Prospec others p Other 2.1 *Indicate the Patients will hat *How will you Check all that Use the S	measures that will be taken to provide prospective research participants with sufficient opportunity to consider whether or nate in the study. apply. (s) of the study staff will meet with the prospective participants/families to review the consent document(s) and/or provide explanation of the study. Individuals will be given a chance to ask questions before making a considered decision about or not to participate in the study. tive participants/families will have the opportunity to take the consent form(s) home and may discuss the documents with rior to deciding whether or not to participate in the study. tive participants will self-administer the consent and send it back if they decide to participate in the study. If you indicated other, describe. length of time subjects are given to decide whether they wish to participate in the study. ave approximately 1-2 weeks from the time of their initial surgical consultation to decide whether they wish to participate in the study assess whether subjects understand the information conveyed during the consent process?
.0	Check all that Member an oral e whether Prospec others p Other 2.1 *Indicate the Patients will hat *How will you Check all that Use the S	measures that will be taken to provide prospective research participants with sufficient opportunity to consider whether or nate in the study. apply. (s) of the study staff will meet with the prospective participants/families to review the consent document(s) and/or provide explanation of the study. Individuals will be given a chance to ask questions before making a considered decision about or not to participate in the study. tive participants/families will have the opportunity to take the consent form(s) home and may discuss the documents with rior to deciding whether or not to participate in the study. tive participants will self-administer the consent and send it back if they decide to participate in the study. If you indicated other, describe. length of time subjects are given to decide whether they wish to participate in the study. assess whether subjects understand the information conveyed during the consent process? apply. Subject Comprehension Tool form for research
